12.7.1. Analyses of Liver Function Tests

Summaries of hepatobiliary laboratory events including possible Hy’s law cases will be provided in addition to what has been described above.

Possible Hy’s law cases are defined as any elevated $ALT > 3 \times \text{Upper Limit Normal (ULN)}$, $\text{total bilirubin} \geq 2 \times \text{ULN}$ and $ALP < 3 \times \text{ULN/missing}$. $\text{Total bilirubin} \geq 2 \times \text{ULN}$ can be within 28 days following the ALT elevation and if direct bilirubin is available on the same day, it must be $\geq 35\%$ of total bilirubin. $ALP < 3 \times \text{ULN/missing}$ means the criteria is satisfied unless the ALP is $\geq 3 \times \text{ULN}$ at any time of bilirubin elevation within the 28 days window.

If data warrant, a summary of liver re-challenges, adaptations and recovery will be provided.

12.8. Other Safety Measures

Vital Signs

Values of vital signs as well as the change from baseline will be summarized by scheduled visit using mean, median, standard deviation, minimum and maximum.

In addition vital signs or blood pressure values will be categorized as follows:

- Systolic Blood Pressure (BP) (mmHg): Grade 0 (<120), Grade 1 (≥ 120 -<140), Grade 2 (≥ 140 -<160) and Grade 3 (≥ 160)
- Diastolic BP (mmHg): Grade 0 (<80), Grade 1 (≥ 80 -<90), Grade 2 (≥ 90 -<100), and Grade 3 (≥ 100)
- Heart rate: <60, 60-100, and >100
- Temperature: <35, 35-38, ≥ 38

Summaries of increase in vital signs or blood pressure from the baseline with respect to the categories defined above will be performed. These summaries will display the number and percentage of subjects with any grade increase, increase to grade 2 and increase to grade 3 in the worst case post baseline only.

Performance Status

ECOG performance status will be summarized at baseline and each post baseline scheduled visit. Summaries will use frequency and percentage of subjects at each planned assessment time. A summary of change from baseline by scheduled visits will be performed, as well as the worst case post-baseline and the best case post-baseline changes during the study (improved, no change, deteriorated).

A supporting listing will also be provided.

EKG

A summary of the number and percentage of subjects who had normal and abnormal (clinically significant and not clinically significant) ECG findings will be displayed by scheduled visits as well as for the worst case post baseline.

The QTc values based on Bazett formula will be rounded to the integer and the values will be categorized into the following ranges: Grade 0 (<450), Grade 1 (450-480), Grade 2 (481-500), and Grade 3 (≥ 501). Summaries of grade increase will be provided. These summaries will display the number and percentage of subjects with any grade increase, increase to grade 2 and increase to grade 3 in the worst case post baseline only.

The changes in QTc values will be categorized into the clinical concern ranges which are specific to changes in QTc: 31-60 and > 60 msec. A summary of change in QTc value will display the number and percentage of subjects with a change within each range in the worst case post baseline only. Subjects with missing baseline values will be excluded from this summary.

The summaries for the QTc will use the calculated value based on Bazett formula.

Listings of abnormal ECG findings and a listing of ECG values will be provided.

LVEF

Absolute change from baseline in LVEF will be summarized in the worst case post baseline only. Only the post baseline assessments that used the same method (ECHO or MUGA) as the baseline assessments will be used to derive the change from baseline. The change from baseline will be categorized as follows:

- Any increase
- No change
- Any decrease
 - 0 - < 10% Decrease
 - 10 - <20% Decrease
 - \geq 20% Decrease
- \geq 10% decrease and \geq Lower limit of normal (LLN)
- \geq 10% decrease and <LLN
- \geq 20% decrease and \geq LLN
- \geq 20% decrease and <LLN

LVEF results will also be listed with subject level details including absolute change from baseline.

Liver Events

For any liver events that occur during the study, the liver event information for Roussel Uclaf Causality Assessment Method (RUCAM) score will be summarized, including whether the subject was age 55 or over, whether the subject became pregnant, liver imaging normal or not, a biopsy was taken or not, whether there was fasting or significant dietary change, whether the subject took any unconventional medications, timing when the event occurs (while on treatment or after stopping treatment) and summary statistics for time from first dose to start of liver event and time from last dose to start of liver event. If the number of events does not support a summary, then only listings will be produced.

For subjects with multiple events, the first event will be used for the summary tables. All events with subject level details will be displayed in a supporting listing.

Ocular Exams

Baseline data will be summarized based on the number and percentage of subjects who receive an ocular exam. As post baseline exams are only performed as clinically indicated data beyond baseline will only be listed.

13. EFFICACY

All efficacy analyses will be based on the ITT population as defined in Section 6 unless otherwise specified. All analyses will be presented by treatment arm.

Efficacy assessments are based on RECIST 1.1, criteria to assess clinical activity and disease status. Primary assessments will be based on imaging data and clinical assessments. Investigator assessments will be considered as primary assessments.

Confirmation of response (i.e., CR and PR) is not necessary per RECIST, version 1.1, as the primary endpoint of the study is not overall best response. The lists of displays for efficacy, including population to use for each display, are shown in Section 18.1.2 of the RAP.

13.1. Primary Efficacy Analyses

No primary efficacy analyses will be conducted in this study.

13.2. Secondary Efficacy Analyses

The primary efficacy endpoint, tumor response including ORR will be reported separately for each treatment arm. In addition a pooled ORR across all treatment arms will also be reported.

Anti-tumor activity will be evaluated based on RECIST 1.1 criteria for solid tumors [Eisenhauer,2009]. Since the primary endpoint of the study is not overall best response, we will generate displays for response irrespective of confirmation status.

The overall response rate (ORR) is defined as the percentage of subjects with a confirmed or unconfirmed complete or partial response by investigator assessment at any time as per RECIST 1.1 criteria. Subjects with unknown or missing response will be treated as non-responders, i.e. they will be included in the denominator when calculating the percentage. An exact 95% confidence interval (Clopper-Pearson) will be computed for this estimate. All data relating to response from the Investigator will be listed including lesion measurements, response assessments and best response.

Waterfall plots of Investigator Assessed Percent Change from Baseline in Tumor Measurement at Time of Best Response will be provided with indications of subject

number below the plot. Waterfall plots will be created for each treatment arm in the study.

13.3. Exploratory Efficacy Analyses

Provided that there are sufficient numbers of events at time of final analysis, we will examine Progression-free survival and duration of response as secondary efficacy endpoints.

13.3.1. Progression-Free Survival

Progression-Free survival (PFS) is defined as the interval of time (in months) between the date of randomization and the earlier of the date of disease progression and the date of death due to any cause. Disease progression will be based on the assessments by the Investigator.

The date of documented disease progression will be defined as the date of disease progression based on either radiographic or clinical data. The date of death should be taken from the Record of Death page. Death on study due to any cause will be included.

If there is no adequate baseline assessment, the subject will be censored at their date of randomization. Subjects without any adequate post baseline tumor assessments will be censored at the date of randomization.

Subjects who progressed or died after an extended period without adequate assessment will be censored at their date of last adequate assessment prior to progression or death even if subsequent information is available regarding progression or death. An adequate assessment is defined as an assessment where the Investigator determined response is CR, PR, or SD. The date of response at that assessment will be used for censoring.

For subjects who receive subsequent anti-cancer therapy the following rules will apply:

- If anti-cancer therapy is started **without documented disease progression or is started prior to documented disease progression**, then PFS will be censored at the date of the last adequate assessment that is no later than the date of initiation of anti-cancer therapy (i.e. if an assessment occurs on the same day as the start of new anti-cancer therapy the assessment will be used - as it will be assumed the assessment occurred prior to the administration of new anti-cancer therapy). The date of response at the last adequate assessment will be used as the censoring value.
- If a subject has only a baseline visit or does not have an adequate assessment that is no later than the date of initiation of anti-cancer therapy, PFS will be censored at the date of randomization.

If a subject has neither progressed nor died nor started new anti-cancer therapy, then PFS will be censored at the date of the last adequate assessment defined as an assessment where the Investigator determined response is CR, PR, SD. The date of response will be used as the censoring date.

A summary of the assignments for progression and censoring dates for PFS are specified in [Table 2](#).

Table 2 Assignments for Progression and Censoring Dates for PFS Analysis

Situation	Date of Progression or Censoring	Outcome
No (or inadequate) baseline tumor assessments (or patients with no post-baseline assessments)	Randomization	Censored
Progression documented between scheduled visits	Date of assessment of progression ¹	Progressed
No progression (or death)	Date of last 'adequate' assessment of response ²	Censored
New anticancer treatment started (prior to documented disease progression). ³	Date of last 'adequate' assessment of response ² (on or prior to starting anti-cancer therapy)	Censored
Death before first PD assessment	Date of death	Progressed
Death between adequate assessment visits	Date of death	Progressed
Death or progression after more than one missed visit	Date of last 'adequate' assessment of response ² (prior to missed assessments)	Censored

¹ The earliest of (i) Date of radiological assessment showing new lesion (if progression is based on new lesion); or (ii) Date of radiological assessment showing unequivocal progression in non target lesions, or (iii) Date of last radiological assessment of measured lesions (if progression is based on increase in sum of measured lesions)

² An adequate assessment is defined as an assessment where the Investigator determined response is CR, PR, or SD.

³ If PD and New anti-cancer therapy occur on the same day assume the progression was documented first e.g. outcome is progression and the date is the date of the assessment of progression). If anti-cancer therapy is started prior to any adequate assessments, censoring date should be the date of randomization.

PFS will be summarized by cohort using Kaplan-Meier curves. Median times to PFS, 1st and 3rd quartiles along with 95% CI, if there are a sufficient number of progressions or deaths, will be estimated using the Brookmeyer-Crowley method [Brookmeyer,1982]. A figure and listing of progression-free survival time will also be provided for each expansion cohort.

A supplementary table showing the details of the number at risk, number of events, and number censored with the event time will also be displayed for each expansion cohort.

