## STUDY DESIGN

Figure 1 Study Schema

This is a three-arm, open label, randomised, Phase II study comparing the upfront combination of dabrafenib (GSK2118436) with trametinib (GSK1120212) versus the combination after eight weeks of monotherapy treatment with dabrafenib or trametinib.

Approximately 54 eligible patients with histologically confirmed cutaneous melanoma that is either metastatic or unresectable (stage IIIc or IV) and BRAF V600E/K mutation positive as determined by a local laboratory will be randomised, 1:1:1 to one of the three treatment arms.

- Arm A: dabrafenib 150mg BID continuously during eight weeks followed by the combination of trametinib 2mg once daily with dabrafenib 150mg BID until disease progression, death or unacceptable toxicity.
- Arm B: trametinib 2mg/day continuously during eight weeks followed by the combination of trametinib 2mg once daily with dabrafenib 150mg BID until disease progression, death or unacceptable toxicity.
- Arm C: trametinib 2mg/day plus dabrafenib 150mg BID continuously until disease progression, death or unacceptable toxicity.

Monitoring will be performed throughout the study according to the Time and Events Table (Table 19). Protocol specified guidelines for dose adjustments, interruptions and discontinuation due to AEs/liver toxicity are provided in Section 5.8, and Section 5.9, respectively. The visits allow a window of +/- 7 days. Dose interruptions should not alter the assessment schedule for any subsequent treatment period.

Biomarker analysis will be performed on blood, tumour and skin samples according to the Time and Events Table (Table 19).

Clinical responses will be evaluated using RECIST 1.1 criteria every 8 weeks. The response evaluation may be performed earlier if clinically indicated (for example, if patient has symptomatic deterioration suggesting rapid disease progression or to confirm clinical response at 4 weeks after achieving response).

Patients who show either radiographic or clinical progression of disease according to the investigator during the monotherapy treatment period in arm A or B will be able to go on to the combination treatment before completion of the 8 weeks monotherapy treatment. Patients will be treated with the combination treatment until disease progression, unacceptable toxicity or withdrawal from study whichever comes first.

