#### 7.3.2.1. Assessment Guidelines

Please note the following:

- The same diagnostic method, including use of contrast when applicable, must be used throughout the study to evaluate lesions.
- The same diagnostic method, including use of contrast when applicable, must be used throughout the study to evaluate a lesion. Contrast agents must be used in accordance with the Image Acquisition Guidelines. All measurements should be taken and recorded in millimeters (mm), using a ruler or calipers.
- Ultrasound is not a suitable modality of disease assessment. If new lesions are identified by ultrasound, confirmation by CT or MRI is required.
- Fluorodeoxyglucose-positron emission tomography (FDG-PET) is generally not suitable for ongoing assessments of disease. It can, however, be useful in confirming new sites of disease when a positive FDG-PET scan correlates with the new site of disease present on CT/MRI or when a baseline FDG-PET was previously negative for the site of the new lesion. Fluorodeoxyglucose (FDG)-PET may also be used in lieu of a standard bone scan providing coverage allows interrogation of all likely sites of bone disease and FDG-PET is performed at all assessments.
- If PET/CT is performed then the CT component can only be used for standard response assessments if performed to diagnostic quality, which includes the required anatomical coverage and prescribed use of contrast. The method of assessment should be noted as CT in the eCRF.

Clinical Examination: Clinically detected lesions will only be considered measurable when they are superficial (e.g., skin nodules). In the case of skin lesions, documentation by colour photography, including a ruler/calipers to measure the size of the lesion, is required.

CT and MRI: Contrast enhanced CT with 5 mm contiguous slices is recommended. Minimum size of a measurable baseline lesion should be twice the slice thickness, with a minimum lesion size of 10 mm when the slice thickness is 5 mm. Magnetic resonance imaging (MRI) is acceptable, but when used, the technical specification of the scanning sequences should be optimised for the evaluation of the type and site of disease and lesions must be measured in the same anatomic plane by use of the same imaging examinations. Whenever possible, the same scanner should be used.

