#### Note:

• Patients with a global deterioration of health status requiring treatment discontinuation without objective evidence of disease progression at that time should be classified as having "symptomatic deterioration." Objective response

status is determined by evaluations of disease burden. Every effort should be made to document the objective progression even after treatment discontinuation.

• In some circumstances, it may be difficult to distinguish residual disease from normal tissue. When the evaluation of CR depends on this determination, it is recommended that the residual lesion be investigated (e.g., fine needle aspirate/biopsy) to confirm the CR.

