# 9.3.5.2. Efficacy Analyses

Efficacy endpoints are described in Section 2 and Section 7.3. The ITT population will be used for the analysis of efficacy data.

The ORR endpoint will be tabulated based on number and percentage of patients attaining a confirmed overall best response of CR or PR in the ITT population. Patients with unknown or missing response data, including those who withdraw from the study without an assessment, will be treated as non-responders (i.e., they will be included in the denominator when calculating the percentage). No imputation will be performed for missing lesion assessment or tumour response data.

Overall response rates (ORR) for each treatment group will be provided along with the corresponding 95% CI. However, ORR will not be compared between treatment groups.

PFS and DoR are exploratory endpoints and will be analyzes provided there is sufficient number of events at the time of final analysis.

PFS will be evaluated for each treatment group. The date of objective disease progression will be defined as the earliest date of radiological or photographic disease progression as assessed by the investigator using RECIST, version 1.1. For patients who have not progressed or died at the time of the PFS analysis, censoring will be performed using the date of the last disease assessment. In addition, patients who start a new anti-cancer

therapy prior to a PFS event will be censored at the date of the last disease assessment prior start of new anti-cancer therapy, respectively. Further details on censoring rules will be outlined in the RAP.

DoR will include patients from the ITT population who achieve a confirmed best response of CR or PR and will only be analyzed provided a sufficient number of patients respond to warrant such an analysis. Censoring rules for duration of response will follow the rules for PFS and will be outlined in detail in the RAP.

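### The PFS progression event is defined in three incompatible ways, so a clinical-only progression can be counted as an event, left at risk, or censored

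*SAP*

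**What the plan says.** **Protocol 9.3.5.2 (Efficacy Analyses).** "The date of objective disease progression will be defined as the earliest date of radiological or photographic disease progression as assessed by the investigator", with RECIST 1.1 as the criterion.

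**SAP 13.3.1 (Progression-Free Survival).** "The date of documented disease progression will be defined as the date of disease progression based on either radiographic or clinical data". Photographic evidence is not mentioned and clinical is not defined. SAP 13 says only: "Primary assessments will be based on imaging data and clinical assessments".

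**SAP Table 2, footnote 1.** Progression takes the earliest of three dates, each the date of a radiological assessment. The first is: "Date of radiological assessment showing new lesion (if progression is based on new lesion". There is no date for photographic or clinical-only progression.

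**Related text.**
- Protocol section 3 sets the trigger for early combination treatment in Arms A and B: "Patients who show either radiographic or clinical progression of disease according to the investigator during the monotherapy treatment period".
- The note to Protocol 7.3.4.4 separates symptomatic deterioration from objective progression: "Patients with a global deterioration of health status requiring treatment discontinuation without objective evidence of disease progression at that time should be classified".
- Protocol 7.3.2.1 covers clinically examined skin disease: "In the case of skin lesions, documentation by colour photography, including a ruler/calipers to measure the size of the lesion, is required".
- Protocol 9.3.5 says departures from the protocol's analysis plan will be documented in the analysis plan and the study report. Nothing in SAP 13.3.1 marks its wording as a departure.

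**The concern.** An event definition should give one answer for each patient. Here the protocol, the SAP text and the SAP's own footnote differ on whether a progression without radiological or photographic RECIST evidence counts, and on how to date it. A programmer could defend more than one coding.

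The design makes this more than a drafting point. The first scheduled lesion assessment is at Week 8. Before then, a declaration of clinical progression in Arm A or B opens the way to the combination; Arm C has no such switch. Treatment is open-label, investigators assess the scans, and Protocol 7.3.2 provides no central review. If clinical-only declarations cluster in the monotherapy weeks of A and B, the choice of rule could alter those arms' early Kaplan-Meier curves more than Arm C's. The same choice carries into DoR, which follows the PFS censoring rules (SAP 13.3.2). It also reaches the optional Cox models in SAP 11.2.1, where starting on combination or monotherapy is a candidate covariate.

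**Working it through.** **1. The plan's own figures.** No PFS event count, median, hazard ratio or power is stated, so there is no PFS figure to reproduce. The stated design figures concern pERK, and they reproduce:
- Half-width at SD 30% and n = 15: t(0.975, 14 df) × 30/√15 = 2.145 × 7.746 = 16.61, as stated.
- Power at SD 70% for an 80% reduction: noncentrality (80/70) × √15 = 4.43, which gives 98.4% by the noncentral t, consistent with the stated >97%.

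Neither depends on the PFS definition.

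**2. One patient under each rule.** Take an Arm A or B patient declared clinically progressed at Week 5, without RECIST progression, who moves to the combination.

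| Rule | Status |
|---|---|
| SAP 13.3.1 sentence, read literally | Event at Week 5 |
| Protocol 9.3.5.2 | Still at risk; the combination is study treatment, so the censoring rule for new anti-cancer therapy does not apply |
| SAP 13.3.1 rule for no adequate post-baseline assessment (no later CR, PR or SD) | Censored at randomisation |
| SAP Table 2, footnote 1 | No date available for the progression |

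**3. The same check in Arm C.** A clinical-only progression on the combination is an event under the SAP sentence. Under the protocol definition the patient remains at risk if treatment continues (Protocol 4.2.1 allows this after consultation). If both drugs stop without progression, the patient is withdrawn and censored (Protocol 7.3.2.2). The conflict therefore exists in all three arms; the early switch exists only in A and B.

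**4. Size per event.** With 54 patients randomised 1:1:1, each arm has 54/3 = 18. One event before Week 8 that the other rule would not count by then moves Week 8 PFS by 1/18 = 5.6 points. Two give 2/18 = 11.1 points and three give 3/18 = 16.7 points. If the Week 8 scan shows RECIST progression anyway, both rules give an event and only the date shifts, by weeks.

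**5. Illustration for the median.** Assumptions: 18 patients, exponential PFS, no censoring, and k patients whose RECIST progression would fall after Week 8 given an event between 0.46 and 1.84 months (Weeks 2 to 8) instead; 20,000 simulated arms. The starting medians of 7.4 and 10.8 months are the combination figures in Protocol 1.1.3, borrowed only to set a scale.

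| k (assumed) | Median, start 7.4 months | Median, start 10.8 months |
|---|---|---|
| 0 | 7.4 | 10.8 |
| 1 | 6.7 | 9.9 |
| 2 | 6.0 | 8.8 |
| 3 | 5.1 | 7.7 |

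The documents give no rate of clinical-only progression, so k is not an estimate.

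**The case against.** The strongest reply is that clinical data in SAP 13.3.1 means RECIST measurement by clinical examination. In cutaneous melanoma this is natural: superficial lesions are measured by ruler or caliper and photographed (Protocol 7.3.2.1 and 7.3.3.1). Protocol 4.2.1 pairs radiographic with clinical progression and adds a reference to RECIST 1.1, and SAP 9.1 repeats this. On that reading the SAP sentence is close to the protocol's. The reading is possible, and it rules out saying that the SAP plainly makes every clinical judgement an event. It does not remove the conflict. Section 3 of both documents uses the same pair of words for an investigator-declared switch with no RECIST condition, and the Table 2 footnote omits photographic dates even on this reading.

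Two stronger inferences are tempting.
- **That the extra events fall only in Arms A and B.** The SAP sentence applies to every arm, and Protocol 4.2.1 foresees clinical progression on the combination, which includes Arm C.
- **That the wording biases PFS against A and B.** The switch gives a reason to declare progression early, but no document shows how often that would occur without RECIST progression. Some such patients might be censored at randomisation rather than counted.

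It is also fair to say that the consequence is limited. PFS is exploratory and analysed only if events suffice, and no treatment comparison is planned (Protocol 9.3.3, SAP 7). That lowers the priority but leaves the inconsistency.

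**Conclusion.** The inconsistency is established from the text: three rules that do not agree, with an undefined term in the SAP. The same clinical-only progressor can be an event, at risk, or censored. The effect on early PFS is 5.6 points per such event in an arm of 18, provided the patient has no RECIST progression by Week 8. How many there would be is unknown. An imbalance against Arms A and B before Week 8 is plausible given the open-label design and the switch rule, but it is not demonstrated, and the problem is not confined to those arms. The reach is descriptive PFS, DoR and the optional Cox models. The pERK analysis, the response rate and the sample size do not change. It should be corrected before the analysis, but it does not threaten the primary result.

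**What to change.** Amend the SAP as follows:
1. Replace the SAP 13.3.1 sentence with the protocol definition: RECIST 1.1 radiological or photographic progression by the investigator, stating that photographed skin-lesion measurement is included.
2. Add photographic assessment dates to Table 2, footnote 1.
3. State how clinical-only progressors are handled in the PFS analysis, with explicit rules for A/B patients who switch early and for patients in any arm who stop both drugs.
4. List clinical-only progressions by arm, with dates.
5. Run a sensitivity analysis that counts clinical-only progression as an event on the date declared.

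The cost is a few lines of SAP text, one listing and one extra PFS run, with no change to patient management. There is a downside. Some clinical-only progressions will move to later scan dates. Others, in patients who stop both drugs, will become censored, possibly informatively, while early switchers stay at risk. The fix could thus introduce an imbalance of its own; the sensitivity analysis in step 5 addresses this by showing how far the curves depend on the choice.

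### SAP 13.3.1: one PFS censoring sentence makes no exception for progression or death, and Table 2 gives a death before any post-baseline scan two opposite outcomes

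*SAP*

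**What the plan says.** SAP 13.3.1 measures PFS from randomisation to progression or death, whichever is earlier, and adds: "Death on study due to any cause will be included". Its censoring rules then include two sentences placed together: "If there is no adequate baseline assessment, the subject will be censored at their date of randomization", and "Subjects without any adequate post baseline tumor assessments will be censored at the date of randomization". The next paragraph explains the key word: "An adequate assessment is defined as an assessment where the Investigator determined response is CR, PR, or SD". Footnote 2 of Table 2 repeats that explanation.

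In SAP Table 2, row 1 covers missing or inadequate baseline assessments and adds in brackets "or patients with no post-baseline assessments"; its outcome is censored at randomisation. Row 5, "Death before first PD assessment", is an event at the date of death. No order of precedence is stated.

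Protocol 9.3.5 censors a patient who starts other anti-cancer therapy before progression or death. Otherwise it censors only where neither progression nor death is documented. Protocol 9.3.5.2 likewise limits censoring to patients without progression or death, apart from new therapy. Both sections leave further censoring detail to the RAP. Section 9.3.5 also requires deviations from the protocol's analysis plan to be documented there, and the SAP does not present this sentence as one.

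**The concern.** Two kinds of patient are affected.

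- **Death before any post-baseline scan.** The patient has no adequate assessment, so the sentence censors at day 0. The PFS definition and the all-deaths sentence make the death an event, and Table 2 supports both answers.
- **PD as the only post-baseline assessment.** PD is not CR, PR or SD, so under the section's own explanation of adequate the sentence again censors at day 0. The PFS definition makes it an event.

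These are the earliest failures. Censored at day 0, they leave the Kaplan-Meier risk set before any event is counted, so the curve describes only patients who got past the first scan and PFS is biased upward. The design foresees such patients: the first scheduled lesion assessment is at week 8, and SAP section 3 lets Arm A and B patients who progress on monotherapy move early to the combination.

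**Working it through.** **Text check.** How each source classifies the two patients, with no new anti-cancer therapy and no more than one missed visit:

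| Source | Death before any scan | Only assessment is PD |
|---|---|---|
| SAP 13.3.1 PFS definition | Event | Event |
| SAP 13.3.1 all-deaths sentence | Event | Not addressed |
| SAP 13.3.1 disputed sentence | Censored, day 0 | Censored, day 0 (adequate = CR/PR/SD) |
| Table 2 row 1 | Censored, day 0 | Does not apply: an assessment exists |
| Table 2 row 5 | Event at death | Not addressed |
| Table 2 row 2 | Not addressed | Covers progression between scheduled visits only |
| Protocol 9.3.5 and 9.3.5.2 | Event | Event |

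For the early death, the SAP contradicts itself in both the text and the table. For PD at the first scan, the sentence stands against the definition and the protocol. Row 1 leans towards an event, but no row names progression at a scheduled visit.

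**Illustrative size, only if the sentence were programmed literally.** The plan gives no PFS event figure to reproduce. Inputs: 18 per arm (54/3); 30.4375 days per month (SAP 9.2.4); median PFS 5.1 months for dabrafenib, 4.8 for trametinib, and 7.4 (all dose levels) and 10.8 (150/2) for the combination (protocol 1.1.1 to 1.1.3); best responses among 77 combination patients of 4 CR, 39 PR, 29 SD and 3 PD (protocol 1.1.3).

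1. Week 8 = 56/30.4375 = 1.840 months.
2. Exponential share with an event by week 8 = 1 − exp(−ln 2 × 1.840/median): 0.221 at 5.1 months, 0.233 at 4.8, 0.158 at 7.4.
3. Check of that model: 0.158 × 77 = 12.2 early events predicted. Observed: 3 with PD as best response, or 5 if the unclassified patients count (77 − 4 − 39 − 29 − 3 = 2). So 3/77 = 0.039 to 5/77 = 0.065. Observed over predicted is 0.246 to 0.410, so the exponential overstates early failure 2.4- to 4.1-fold.
4. Arms A and B, scaled by that ratio: 0.221 × 0.246 = 0.054 to 0.233 × 0.410 = 0.096, which is 1.0 to 1.7 of 18.
5. Arm C, from the observed share: 0.039 to 0.065, which is 0.7 to 1.2 of 18.
6. Survival from week 8 to week 16 at the 10.8-month hazard (assumed for all arms) = exp(−ln 2 × 1.840/10.8) = 0.889. With early share p, 16-week PFS is (1 − p) × 0.889 if early events count, and 0.889 if those patients are censored at day 0.
   - Arms A and B: 0.946 × 0.889 = 84% to 0.904 × 0.889 = 80%, reading as 89%.
   - Arm C: 0.961 × 0.889 = 85% to 0.935 × 0.889 = 83%, reading as 89%.

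For a given early share, these counts are upper bounds on the patients caught: someone who progresses first, stays on treatment and is later rated CR, PR or SD does have an adequate assessment.

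**The case against.** The strongest reply is that the intended meaning is plain. The sentence just before the disputed one speaks of an adequate baseline assessment, and a baseline scan cannot be CR, PR or SD, so adequate may mean something like evaluable there. On that reading PD at the first scan is adequate and counts as an event. Row 1 fits this, since it asks only whether any post-baseline assessment exists. Row 5 names death and row 1 does not, so the specific row should govern. The section's final censoring rule is expressly limited to patients without progression, death or new therapy. The protocol leaves detail to the RAP, and SAP 9.2 refers derivations to separate dataset specifications, which are not among the documents and may settle the matter.

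Much of this stands. The PD part is the weaker one, and the intent can be inferred. It does not remove the defect. The only explanation of adequate that the section gives is CR, PR or SD, stated twice. The early-death conflict does not depend on that word at all, and a pre-specified censoring rule should not rely on a programmer overriding what it says.

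Three stronger readings are tempting but not supported:

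- **That the section as a whole censors every early failure.** Only one sentence lacks the exception; the definition, the all-deaths sentence and the death rows of Table 2 point the other way.
- **That all these patients drop out of the exploratory Cox model of PFS in SAP 11.2.1 because of this rule.** Its covariate is the H-score decrease on reaching combination therapy, summarised from week 8 to week 10 in Arms A and B. A patient in those arms who dies before then has no value and is absent under either rule. Only patients with a decrease value are affected.
- **That about 4 of 18 patients in Arms A and B would be lost.** The unscaled exponential gives this (0.221 × 18 = 4.0; 0.233 × 18 = 4.2), but step 3 of the check shows that model overstates early failure.

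**Conclusion.** The point holds as a defect in wording. The disputed sentence, followed as written, gives a result that conflicts with the SAP's PFS definition and with protocol 9.3.5 and 9.3.5.2. Table 2 leaves a death before any post-baseline scan both censored and an event. PD at the first scan is a literal conflict with the sentence, while Table 2 and the definition favour an event.

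The size is roughly 1 to 2 patients of 18 per arm, and only under literal programming. It rests on background studies rather than trial data: an early-PD ratio from an all-dose combination cohort carried over to monotherapy, best response of PD taken as an event by week 8, that study's scan schedule unknown, and one assumed hazard after week 8.

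The consequence is limited. PFS is exploratory, analysed only with sufficient events, and not compared between arms; the primary p-ERK endpoint and ORR are untouched. Duration of response is largely unaffected, since every responder has a CR or PR assessment. It is still worth correcting before PFS is programmed.

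**What to change.** 1. Reword the sentence to: *Subjects with no adequate post-baseline assessment and no documented progression or death are censored at randomisation.*
2. Apply the same limit to the post-baseline part of Table 2 row 1.
3. State that PD at the first assessment and death before the first assessment are events, subject to the existing rules on new anti-cancer therapy and on more than one missed visit.

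Optional tidying: the second new-therapy bullet, for a patient who "does not have an adequate assessment that is no later than the date of initiation of anti-cancer therapy", and the last sentence of footnote 3 could carry the limit that row 4 already has ("New anticancer treatment started (prior to documented disease progression"). Row 7 could say what date applies when no adequate assessment exists.

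The cost is wording only: one sentence, one table row and one clarifying statement, plus the optional edits. No new data and no protocol amendment are needed.
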